5.1 Patient Recruitment

All adult cardiac surgery eligible patients will be fully informed of what the study entails and will be provided with written patient information sheet on the study. Urgent in patient will be approached in the cardiology ward 1 to 2 weeks after the surgical referral and they will be given more than 48 hours to consider whether they wish to take part. Elective patients will be approached at the outpatient clinic which is 4 to 6 weeks prior to the surgery.

5.2 Patient Consent

Elective patients will be approached by the cardiac surgeon during their outpatient clinic appointments. Urgent in patient will be approached by the cardiac surgeon in the cardiology ward. Potential participants are required to read the Participant Information Sheet. Fully informed written and verbal consent will be gained on admission to cardiac surgery ward 24 hours before the surgery is undertaken. A copy of the completed consent form will be given to the participant.

All participants will be informed that they may withdraw from the study at any point without giving a reason.

6 DATA COLLECTION AND DATA ANALYIS

6.1 Data Collection

Patient data: Generic

- All preoperative clinical data of patient demographics will be obtained from the patients' clinical notes, clinical database, laboratory reports.
- The STAI and cortisol outcomes will be measured for this study at 4 time points pre- and postsurgery.

Clinical patient data:

All clinical data will be collected by research team members.

All the clinical data will be collected prospectively into a relational database. General demographics including age, sex, race, body mass index, hospital admission.

Data collection: Please note that the questionnaires, STAI, (Table 1) will be applicable to both study arms.

Demographic factors

All basic pre and post operative variables will be collected such as on age and gender, duration of the surgery, medications, consumption of alcohol, tobacco and type of cardiac surgery. Alcohol and tobacco consumption will be recorded as withdrawal symptoms could also influence the participant's behaviour postoperatively.

Time points of collecting anxiety STAI scores and cortisol assay:

Control/VR intervention group:

The first and second set of STAI questionnaire and cortisol assay swab will be collected before and after the control/VR session within 30 minutes after the control/intervention. The third and fourth set of STAI questionnaire and cortisol swab will be collected on day 3 post-surgery around 6 pm before and after the control/VR session within 30 minutes.

Physiological variable

We will record heart rate, blood pressure and respiratory rate at baseline (pre-surgery), before and after the VR intervention, post-surgery to assess the changes and compare between the two groups. We will record same physiological assessment for the control group before and post-surgery. The time period of the assessment will be matched as similar as possible to reduce any bias.

Psychological variable

State-Trait Anxiety Inventory (STAI) will be used to measure patients' self-evaluation stress and anxiety. It is a set of 20 statements with scores 1 to 4 which people have used to describe how they feel "at this moment."

It will be collected pre- and post-surgery and at the same time points for both groups to assess any difference in anxiety between groups.

In addition,

- VR experience for pre- and post-surgery.

Absorption is the "tendency to become fully involved in a perceptual, imaginative, or ideational experience". We will ask the intervention subjects to answer this question: "Could you estimate on a 0- (not at all) to 10- (fully) scale how deeply you felt absorbed and felt your attention as focalised and focused by the experience you have just lived?". Immersion and presence will be assessed using a Visual Analogue Scale. The questions will be of the form "from 0 to 10, how much did you feel present in the environment?"

Cortisol assay:

Both group patients will have 4 samples, before and after control/VR intervention pre- and postsurgery which will give a total of $4 \times 30 = 120$ samples.

Sample collection:

- Salivary cortisol is considered a reliable and valid measure of unbound or free cortisol levels in plasma. Oral swabs (30 x 10mm cylinder) and salivette storage tubes will be used to collect samples from the participants. During collection, participants will be instructed to place the swab under their tongue on the floor of the mouth for 1-2 minutes. Swabs will be placed in salivettes and within an hour after collection, stored in a lab freezer below -20°C. The storage, transport and testing procedures or the samples will be subject to standard practice and all usual risk assessment procedures as per MFT hospital.

Analysis:

The Cortisol free in Salvia ELISA kit will be used to determine the concentration of cortisol in the samples. Upon the receipt of the samples, they will be immediately stored at -20°C until analysis. The frozen samples will be thawed and centrifuged for 5 to 10 minutes at 2000-3000 x g. Of the standard and reagent, the control reagent, and the saliva sample,50 µL will be dispensed in microtiter wells, as well as 50 µL of a cortisol-horseradish peroxidase conjugate for binding to the coated antibody. The wells will be incubated for 60 minutes at room temperature. Afterwards, they will be rinsed 3 times with 300 µL diluted wash solution and 200 µL of substrate solution will be added. Again, the wells will incubate for 30 minutes at room temperature and 50 µL of stop solution will be added to each well. The absorbance of each well will be determined with the use of a microtiter plate calibrated reader at 450 \pm 10 nm within 15 minutes.

6.2 Sample size and power calculation

Sample size has been determined on pragmatic grounds and rule of thumb for pilot studies. 15 patients are required in each group giving a total of 30 patients. We decided to enrol 10% more to compensate for dropouts after the surgery making the total 34 patients.

6.3 Planned Statistical analyses: Clinical

Analyses will be mainly descriptive. Any test will be for exploratory and for hypothesis generating purposes. Proportion of consent and dropouts and their 95% CI will be reported. Demographics, baseline, physiological and medical characteristics will be summarised for the whole cohort and for each arm separately. Summary statistics of anxiety and stress score and cortisol levels will be provided at each time point (baseline and day 3 post operatively) for each arm.

Number of patients approached and proportion consenting to participate will be reported.

Number and percentage of patients removed due to ventilation will be reported.

Number and percentages of patients not completing VR session for any reason will be reported.

Pre and post operation anxiety scores will be compared between the two groups using t-test or equivalent non-parametric test. Pre and post operation cortisol levels will be compared between the two groups using t-test or equivalent non-parametric test. Changes in stress scores and cortisol levels will be assessed. Pre and post operation cortisol levels and anxiety scores will be correlated for all and for each arm separately.

Result from VR experience and VR absorption for the intervention group will be summarise.

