In addition, we will explore if there is association between salivary cortisol levels as a potential biomarker for stress and self-completed questionnaires anxiety level (STAI). We will obtain four samples of before and after control/VR intervention pre- and post-surgery to see the co-relation.

Expected outcomes:

This study will identify whether the use of VR technology has the potential impact to reduce pre and post operative anxiety and stress.

2. Research Question

- 1. Can immersive head mounted Virtual Reality headset intervention reduce pre-and postoperative anxiety and stress in adult patients undergoing elective cardiac surgery?
- 2. Is the use of VR technology being feasible immediate post-surgery on cardiac surgery patients?

3 Objectives and Outcomes assessments

2.1 Primary Objectives:

Assessment of anxiety, stress levels between two groups

2.2 Secondary Objectives:

- Feasibility of VR technology.
- Correlation between cortisol level and STAI
- VR experience
- VR absorption

2.3 Outcome Measures:

- **Primary outcome:** patients' anxiety and stress levels four time points (before and after each session on pre- and post-surgery (STAI)
- Secondary outcomes:
- Cortisol swabs four time points (before & after each session on pre- and post-surgery).
- Physiological parameters pre- and post-surgery.

For intervention group only:

- Patient experience about VR (Rescape™ company questionnaire))
- VR Absorption and immersion scale (VAS 0-10)
- Proportion of patients consenting to VR.
- Proportion of patients completing the VR sessions.
- Adverse events due to VR.

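### Section 6.3 names two time points for a four-time-point primary outcome and leaves open which STAI score is compared between arms, with no pre-session adjustment specified

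*Protocol*

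**What the plan says.** Section 2.3 (Outcome Measures) defines the primary outcome as "patients' anxiety and stress levels four time points (before and after each session on pre- and post-surgery (STAI"). Section 6.1 (Data Collection) agrees: "The STAI and cortisol outcomes will be measured for this study at 4 time points pre- and postsurgery". It then sets the schedule. For the pre-surgery session, "The first and second set of STAI questionnaire and cortisol assay swab will be collected before and after the control/VR session within 30 minutes"; for the second session, "The third and fourth set of STAI questionnaire and cortisol swab will be collected on day 3 post-surgery around 6 pm", again before and after the session. I call these four scores T1 to T4.

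Section 6.3 (Planned Statistical analyses: Clinical) says that summary statistics of the anxiety and stress score and of cortisol "will be provided at each time point (baseline and day 3 post operatively) for each arm". The between-arm comparison is one sentence: "Pre and post operation anxiety scores will be compared between the two groups using t-test or equivalent non-parametric test". A parallel sentence covers cortisol. A further sentence promises an assessment of changes in stress scores and cortisol, without giving the interval, the between-arm contrast or the method. The section opens by calling the analyses mainly descriptive and any test exploratory.

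**The concern.** There are two STAI scores on each side of surgery, and they answer different questions. T1 precedes any session, so a difference between randomised arms at T1 is chance. T2 carries the effect of session 1. T3 carries whatever of session 1 persists through surgery. T4 carries the total effect after both sessions. A plan that speaks of a pre-operation and a post-operation score has not said which of these it will compare, and a list of two time points cannot describe an outcome measured at four.

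Two things are at stake. First, the contrast that answers research question 1 is not fixed before the data are seen; the choice between T1 and T2, and between T3 and T4, remains open. Second, the pre-session score is due to be collected from every patient, yet the comparison sentence does not use it. With 15 per arm, an unadjusted comparison carries the full between-patient variance and any chance imbalance at T1.

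**Working it through.** **The plan's own figures.** Section 6.2 gives 15 per arm, 30 in total, and 34 after a 10% dropout allowance: 30 / (1 − 0.10) = 33.3, rounded up to 34. This reproduces and is not affected by the point. Section 6.1 counts 4 × 30 = 120 cortisol samples, which confirms four time points per patient.

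**Time points side by side.**

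| Place | STAI time points |
|---|---|
| 2.3 Outcome Measures | four: before and after each of two sessions |
| 6.1 Data Collection | four: sets 1 and 2 at session 1, sets 3 and 4 on day 3 |
| 6.3, summaries | two: baseline and day 3 |
| 6.3, between-arm test | one pre-operation and one post-operation label; score not identified |

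**What the test means under each reading.**

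- Pre-operation score = T1: the arms are compared before any intervention, so no session effect can appear, and T2 has no stated comparison.
- Pre-operation score = T2: a valid, unadjusted comparison after session 1.
- Post-operation score = T3: carry-over from session 1 only.
- Post-operation score = T4: a valid, unadjusted comparison after both sessions.

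**Precision.** The protocol states no SD and no correlation, so both are assumptions: SD 10 points, and correlation r between the covariate and the outcome from 0 to 0.8. There are 15 per arm, N = 30.

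Unadjusted 95% CI half-width: t(0.975, 28) × SD × √(2/15) = 2.048 × 10 × 0.3651 = 7.48 points.

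ANCOVA half-width: t(0.975, 27) × SD × √(1 − r²) × √(2/15) × √(1 + 1/26). The last factor is the average cost of chance imbalance in the covariate, 1 + 1/(N − 4). Without the r term this is 2.052 × 10 × 0.3651 × 1.019 = 7.64.

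Change-score half-width: 7.48 × √(2(1 − r)).

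| r | Unadjusted | ANCOVA | Change score |
|---|---|---|---|
| 0 | 7.48 | 7.64 | 10.58 |
| 0.3 | 7.48 | 7.28 | 8.85 |
| 0.5 | 7.48 | 6.61 | 7.48 |
| 0.7 | 7.48 | 5.45 | 5.79 |
| 0.8 | 7.48 | 4.58 | 4.73 |

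All half-widths scale with the SD. ANCOVA breaks even where √(1 − r²) = 7.48 / 7.64 = 0.98, that is at r of about 0.2. The change score beats the unadjusted comparison only if r exceeds 0.5.

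**The case against.** The strongest reply is that the protocol uses pre- and post-surgery as labels for two occasions, each holding a before and an after score. Sections 2.3 and 6.1 both do so. On that usage the comparison sentence in 6.3 can cover all of T1 to T4, and T2 is itself a pre-operation score. This stands: a reader might infer that the primary outcome goes unanalysed, or that one planned test has a true null by design, but the text does not establish either. Both follow only if the pre-operation score is T1.

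A reader might also infer that the pre-session score is never used. That goes too far. Section 6.3 plans to assess changes in stress scores, and 6.1 names STAI as the measure of both stress and anxiety, so a STAI change may be intended. The sentence does not close the gap, because it could equally mean a change within a session or from before to after surgery.

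It is also fair that an unadjusted t-test in a randomised comparison is valid, that model form is often left to an SAP (one may exist and is not shown), and that the gain is small at low correlation. A low r is plausible between T1 and T4, which lie on either side of surgery. Finally, the pilot has no powered hypothesis, so lost power carries little weight. These replies bear on how serious the point is. They do not remove the mismatch between four time points and two inside one document.

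**Conclusion.** The point holds in limited form. Section 6.3 does not match the four-time-point primary outcome, does not identify which score on each occasion is compared between arms, and specifies neither a pre-session adjustment nor a defined between-arm change. The mismatch rests on the text alone and needs no assumption.

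The size of the precision gain does rest on assumptions. At SD 10 and 15 per arm, adjustment takes the half-width from 7.5 points to about 7.3 at r = 0.3 and 4.6 at r = 0.8; if r is near 0 it widens very slightly, to 7.6.

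Because the tests are declared exploratory and the sample size was set by rule of thumb, the documents do not support calling this an invalid test or a failure of a confirmatory analysis. It is a low-cost improvement in clarity and precision.

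**What to change.** Reword section 6.3 as follows.

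- Summarise STAI by arm at T1, T2, T3 and T4.
- Replace the t-test sentence with two models: ANCOVA of T2 on arm adjusted for T1 (session 1 effect), and ANCOVA of T4 on arm adjusted for T1 (total effect at day 3). Report each as an adjusted mean difference with 95% CI. T1 is the covariate in both because T3 is measured after randomisation and may already reflect session 1.
- Define change as T2 − T1 and T4 − T3, reported by arm, and note that T3 is post-randomisation.
- Do not test the arms against each other at T1.
- Use the same time-point structure for cortisol.

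The cost is the rewording and one degree of freedom per model (28 to 27), with the very slight widening shown above if r is near 0. No additional data are needed, since all four scores are already scheduled.

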6.4 Data analyses and Study Stopping Criteria

Data will be analysed at the end of the study. Any serious Major Adverse events such as severe dizziness, severe skin rashes, severe confusion related to the VR application which requires emergency hospital admission/treatment will trigger study stopping criteria and will be discussed immediately at an emergency steering and data monitoring committee. The final clinical data will be analysed at the study end point.

6.5 Data Confidentiality and security

All data will be kept strictly confidential according to Good Clinical Practice (GCP) Guidelines. All data will be anonymised using unique study reference numbers for each patient.

Excel spreadsheets used for the study, including the recruitment log in excel, will be saved under a study folder that will be permissions based as to who can amend and view the data within the study team. These will be stored on Trust encrypted password protected devices within MFT recruitment site.

All personal identifiable participant information will be destroyed securely and immediately at the end of the research according to the local hospital research protocol. All study data will be stored by the Manchester University NHS Foundation Trust in a secure fashion for 10 years in accordance with the ICH GCP. The trial data and documentation will be archived as per the University of Salford archiving SOP.

Further details can be found in the Data Management Plan held by the University of Salford as study sponsor.

7 SAFETY REPORTING

We are not expecting any major adverse events for this study. However, if there are any adverse events, including serious adverse events (SAE), that the chief investigator suspects could have been related to procedures in the study protocol will be reported to the study Sponsor.

All adverse event assessments and reporting will be carried out in line with MFT trust and the University of Salford SOP's. The serious adverse events are defined as an adverse event which results in one of the following:

- a. Severe confusion which requires immediate hospital admission and treatment.
- b. Severe dizziness or headache which requires immediate hospital admission and treatment.

 Severe skin or allergic rashes which requires immediate hospital admission and treatment.

Serious adverse events and adverse events will be collected and recorded on the electronic case report form according to the local hospital research protocol.

The main role of the Principal investigator (PI) will report any adverse and serious adverse events:

- a. Using medical judgement in assigning seriousness, causality and whether the event/reaction was anticipated.
- b. Ensuring that all SAE/SARs are recorded by completing the SAE form as soon as possible after becoming aware of the event and send a scanned copy to the University of Salford sponsor office using the email address [contact]
- c. SAE/SARs must be reported to the sponsor office within 24 hours of the research team becoming aware of the event.
- d. Reviewing and reporting the accuracy and completeness of all SAE/AE.
- e. Closely monitoring patients for any new events.
- f. Ensuring a log of all events is kept within the Site File and which may be reviewed by oversight committees such as the Steering Committee.

The Chief Investigator (CI) is responsible for:

- a. Clinical oversight of the safety of patients participating in the trial, including an ongoing review of the risk / benefit.
- b. Using medical judgement in assigning the SAEs/SARs seriousness, causality and whether the event was anticipated where it has not been possible to obtain local medical assessment.
- c. Using medical judgement in assigning whether an event/reaction was anticipated or expected.
- d. Immediate review of all Serious Unexpected Serious Adverse Reactions (SUSARs).
- e. Review of specific SAEs/SUSARs in accordance with the protocol and trust SOPs on Safety Reporting for Studies other than Clinical Trials of Investigational Medicinal Products (CTIMPs).
- f. The Investigator is expected to maintain a log or spreadsheet of all adverse events and effects (including those reported as serious), which may be reviewed by oversight committees such as the Steering Committee. Any trends must be reported by the Investigator to oversight committees in a timely manner.

7.1: Expected safety reporting.

Cross contamination and patient reported side effects from VR headset use will be reported such as severe nausea, severe dizziness, severe disorientation, severe balance problems, severe headache, severe eye strain, severe fatigue and severe cross infection which requires immediate medical treatment.

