This project is a pilot study Virtual Reality mindfulness and wellbeing study, the medical statistician will be an independent person, [name] and [name]. The DMC will meet by Skype or teleconference as much as possible for sustainability. However, if there are number of any adverse events or serious adverse events reported such as severe dizziness, severe skin rashes, severe confusion related to the VR application, the data will be looked into at any time of the study period. Procedure will be conducted in accordance with MHRA Good Clinical Practice Guide. The committee will have full access to the anonymous data after approximately 10% to 25% of participants have been recruited. The aim of the DMC is to identify any safety issues that may give cause for concern and to inform the study Steering Committee (including early study termination, if required). The DMC will meet before the Steering Committee (SC) meeting and the minutes from the DMC will be forwarded to the SC for their consideration. The role of the committee will be to monitor and advise the study safety.

Steering Committee

The Steering committee will be independent to the DMC. The plan for steering committee to meet at least once to make sure that there are no reports of an unexpected events such as severe confusion, severe dizziness unable to recover which requires emergency admission due to VR application during the study period. The committee will be chaired by the Clinical surgical experts, [name], and a lay person, all of whom will be completely independent of the study. The lay person who is our previous heart patient who sits on a Ticker club (heart charity club) at Wythenshawe hospital will be given full training about this study.

ABBREVIATIONS

3D 3 Dimensions

GP General Practitioner

STAI State Trait Anxiety Inventory

[figure not shown]
VAS Visual Analogue Scale

VR Virtual Reality

STUDY FLOW CHART

STUDY PROTOCOL

1 Abstract

Background (Lay):

Non-drug methods like hypnosis and Virtual Reality (VR) are used alongside other treatments to help patients with anxiety and different types of pain. But when it comes to using VR to help people who are having heart surgery, there haven't been many studies. One reason for this might be that using VR for this purpose is relatively new, VR technology is changing quickly, and it can be expensive to get started with VR.

Scientific

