8.2 End of the study

The end of the final data capture will be of the last patient data collecting point which is day 3 at 6 pm, from the day of patient surgery. There will be no data will be obtained from any research participants after this date.

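### The serious-event definition requires hospital admission of patients already in hospital, and data capture is set to end at the hour of the second VR session

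*Protocol*

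**What the plan says.** Section 7 of the protocol introduces its list with "The serious adverse events are defined as an adverse event which results in one of the following". Three items follow: "Severe confusion which requires immediate hospital admission and treatment", "Severe dizziness or headache which requires immediate hospital admission and treatment" and "Severe skin or allergic rashes which requires immediate hospital admission and treatment". SAEs and SARs must reach the sponsor office within 24 hours of the team becoming aware of them.

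Three other places describe severe VR reactions in different terms:

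- Section 6.4, on major events related to VR: "which requires emergency hospital admission/treatment will trigger study stopping criteria".
- The Steering Committee text at the front: "unable to recover which requires emergency admission due to VR application".
- Section 7.1, on expected side effects: "severe cross infection which requires immediate medical treatment", with no mention of admission.

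Section 5.2 takes consent on admission to the cardiac surgery ward, 24 hours before the operation. Section 5 schedules session one within an hour of surgery and session two on postoperative day 3 at about 6 pm, with the headsets used only on hospital premises. Section 2.3 lists adverse events due to VR among the outcomes for the intervention group.

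Section 8.2 puts the last data point at day 3, 6 pm, and adds: "There will be no data will be obtained from any research participants after this date".

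**The concern.** All three items join admission and treatment with 'and', so both are needed. A patient who is already in a bed can need treatment but cannot need admitting. The list is also worded as complete: a death or a prolonged stay after cardiac surgery does not appear in it.

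Two things are at stake. The first is the serious label and the 24-hour report that depends on it. The second is what the study can say about safety: a result of no SAEs would come largely from the definition and would be weak evidence that the headset is safe. The section 8.2 cut-off adds to this, because it falls at the second exposure, while rash (section 7) and cross infection (section 7.1) are named as harms and the headsets are reused between patients.

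**Working it through.** **Can a participant meet the section 7 definition?**

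1. Session one: the patient has been on the ward for about 24 hours and is within an hour of surgery, so is admitted.
2. Session two: the patient is on postoperative day 3 and the headset stays on hospital premises, so is admitted.
3. Each section 7 item requires admission and treatment. The admission part is false at both sessions for a patient who is already in.
4. Only readmission after discharge would satisfy the wording. That would almost always fall after the section 8.2 cut-off.

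**The four thresholds, applied to one case: severe dizziness on the ward, caused by VR and needing urgent treatment**

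| Place | Condition | Met by an inpatient? |
|---|---|---|
| Section 7 (SAE) | admission and treatment | No, read literally |
| Section 6.4 (stopping) | admission/treatment | Yes, if the slash means 'or' |
| Steering Committee text | emergency admission | No, read literally |
| Section 7.1 | immediate medical treatment | Yes |

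The same event is reportable under one section, may trigger stopping under another, and is not serious under a third.

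**Time left after session two**

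Inputs: start 18:00 (sections 5 and 8.2; the protocol says 'around', so the exact hour is an assumption), session length 15 minutes (section 5), post-session STAI and swab within 30 minutes (section 6.1).

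- Session ends: 18:00 + 15 min = 18:15.
- Fourth STAI and swab, at the latest: 18:15 + 30 min = 18:45.
- Cut-off at 18:00: 18:00 − 18:15 = −15 min. Capture closes before the session ends and before the protocol's own fourth measurement.
- Cut-off at the last measurement: at most 30 min of observation.
- Cut-off at midnight, reading 'date' as the calendar day: 24:00 − 18:15 = 5 h 45 min, about 6 hours.

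**Numbers of patients**

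The plan's total of 34 reproduces as 30 / (1 − 0.10) = 33.3, rounded up to 34. The conclusion does not depend on it. With equal allocation, 15 to 17 patients wear the headset.

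For scale, with zero events among n patients the one-sided 95% upper bound on the event rate is 1 − 0.05^(1/n): 18.1% for n = 15 and 16.2% for n = 17. This is all that zero events would show under a definition that works. Under the section 7 wording it does not show even that.

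**The case against.** A reader might infer three stronger points, and the documents do not support them.

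- *That inpatients cannot trigger the stopping criteria.* Section 6.4 has a slash between admission and treatment, so emergency treatment alone may be enough. The DMC text also allows the data to be examined at any time for severe dizziness, rash or confusion related to VR, with no admission condition. The section 6.4 wording is ambiguous and out of line with the other places, but it can be met.
- *That VR harms go uncounted.* Non-serious events also go on the electronic case report form and into a log. Any event that the chief investigator suspects is related to study procedures is reported to the sponsor. Section 5 records side effects that lead a patient to stop, section 7.1 covers severe ones, and the section 2.3 outcome counts adverse events, not SAEs. Before the cut-off, what is lost is the serious label and the 24-hour clock.
- *That every participant has zero observation after session two.* That needs the most literal reading of an approximate time and of a clause headed as the end of the study. The clause may mean the last patient's day 3, in which case capture for earlier patients is not closed that evening. Even so, the last patient has almost no window, and no adverse-event period is stated for anyone.

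Two further defences deserve weight. The principal investigator assigns seriousness by medical judgement, and section 7 refers to Trust and sponsor SOPs, which are not shown and may define seriousness in the usual way. Both soften a literal reading. Neither removes the problem: judgement is exercised against a written list that inpatients cannot satisfy, and if the SOPs differ from that list, the protocol contradicts the procedures it says it follows.

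**Conclusion.** The section 7 definition is wrong as written. Read literally, no participant in hospital can meet it, in either arm (30 to 34 patients); for VR reactions, 15 to 17 patients are concerned. The effect is that severe reactions are classed as non-serious and the 24-hour report does not start. They do not vanish from the record.

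The threshold is stated in four different ways and must be reconciled. The documents do not show which version was intended, and this review does not choose one.

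Section 8.2, read literally, conflicts with the fourth STAI and swab. It leaves from no time to about 6 hours to see harms after the second exposure, on the assumption that it applies to each participant and that session two starts at 18:00. Under the end-of-study reading the window is undefined.

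The conclusion on seriousness assumes that participants stay in hospital from admission to the evening of day 3, as the session plan requires, and that the unseen SOPs do not expressly override the list.

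**What to change.** 1. **Section 7.** Replace the three-item definition with the seriousness criteria of the sponsor and Trust SOPs that the section already invokes, so that it can apply to patients already in hospital. Keep the three listed reactions as events of special interest.
2. **Steering Committee text, sections 6.4, 7 and 7.1.** Bring the wordings into agreement, or state where they are meant to differ. The sponsor chooses the threshold.
3. **Section 8.2.** Set the end of outcome collection after the fourth STAI and swab. State a separate, later end of adverse-event collection for each participant, for example by review of routine notes to discharge.

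The cost is protocol and case-report-form wording and, if the notes review is adopted, a short task for 30 to 34 patients. More background surgical SAEs will enter the count, so the safety table will look less favourable, but a low count of VR-related events would then mean something.
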